7.2.1.1 X-ray of Impaired Joints

A subject listing for x-rays of impaired joints will be presented using the SAS. No summary table presentation is planned for X-ray results.

The following information item is obtained from the eCRF:

- X-ray of impaired joints (*X-Ray of Impaired Joints* eCRF panels).

7.2.2 Haemophilia Symptom (Haemo-SYM) Questionnaire

The haemophilia symptom questionnaire (Haemo-Sym) is a self reported instrument of measuring symptom severity in patients with haemophilia and has two subscales: pain and bleeds. Lower Haemo-SYM scores indicate fewer symptoms. Therefore, negative change scores indicate that symptoms have improved.

The questions in the Haemo-Sym questionnaire are assigned to the subscales of pain and bleeds as set out in Table 2:

Table 2 Haemo-Sym Questionnaire Subscales

Question (Severity of...)	Subscale
Spontaneous bleeding in my joints (unrelated to injury or activity)	Bleed
Spontaneous bleeding in my muscles (unrelated to injury or activity)	Bleed
Prolonged bleeding after injury in spite of treatment	Bleed

Question (Severity of...)	Subscale
Intense pain because of bleeding event	Bleed
Pain because of swelling in my joints	Pain
Joint pain due to active bleed	Bleed
Bleeding during personal hygiene routine (during shaving, tooth brushing or flossing)	Bleed
Pain because of climbing stairs	Pain
Pain upon waking in the morning	Pain
Constant pain	Pain
Pain because of active arthritis	Pain
Pain in my muscles	Pain
Pain that needs medication	Pain
Joint sensitivity to weather conditions	Pain
Reduced range of joint movement	Pain
Joint deformity	Pain
Sleep disturbance because of pain or bleeds	Pain
Blood in my urine	None
Nose bleeds	None

Results are assigned scores as follows:

- Absent = 0.
- Very mild = 1.
- Mild = 2.
- Moderate = 3.
- Severe = 4.
- Very severe = 5.

The following derivations will be made based of the subject diary reported results:

- The score for each subscale is determined only if at least 50% of the results in that subscale is available. The score should be determined as:

$$Score = \frac{MeanScore}{5} \times 100$$

where MeanScore is the mean of the available results in the particular subscale. If less than 50% of the results in a subscale is available, then no score will be calculated for that subscale.

- The total score for the Haemo-Sym questionnaire should be determined as the mean score of the two subscales should both subscale scores be available.

Within treatment arm change and between treatment arm change in Haemo-SYM total score as well as bleed and pain severity between baseline and completion will be tested for any statistical significant differences in a similar manner as described in Section 7.2.1: Haemophilia Joint Health Score (HJHS) Questionnaire.

Items to be included in these tests as part of the secondary efficacy outcomes are:

- Change in Haemo-SYM total score.

Items to be included in these tests as part of the exploratory efficacy outcomes are:

- Change in bleed severity total score.
- Change in pain severity total score.

7.2.3 Short-Form 36 (SF-36) Questionnaire

The Short-Form 36 (SF-36) is a self-administered, validated questionnaire designed to measure general health related quality of life. The questionnaire is divided in eight domains including: physical functioning, role-physical, bodily pain, general health, vitality, social functioning, role emotional and mental health. From this questionnaire two summary scores can be calculated, the physical component score and the mental component score.

Information on the SF-36 is obtained from electronic patient diaries as supplied by the third party vendor eRT.

The questions in the SF-36 are assigned to domains and scored as set out in Table 3.

Table 3 SF-36 Scoring for Individual Questions

Question	Domain	Score
1. In general, would you say your health is:	General Health (GH)	Excellent: 5 Very Good: 4.4 Good: 3.4 Fair: 2 Poor: 1
2. Compared to one year ago, how would you rate your health in general now?	No Scale	Much better now than one year ago: 1 Somewhat better now than one year ago: 2 About the same as one year ago: 3 Somewhat worse now than one year ago: 4 Much worse now than one year ago: 5
3. The following questions are about activities you might do during a typical day. Does your health limit you in these activities? If so, how much?		

Question	Domain	Score
3a. Vigorous activities	Physical Functioning (PF)	Yes, limited a lot: 1 Yes, limited a little: 2 No, not limited at all: 3
3b. Moderate activities	Physical Functioning (PF)	Yes, limited a lot: 1 Yes, limited a little: 2 No, not limited at all: 3
3c. Lifting or carrying groceries	Physical Functioning (PF)	Yes, limited a lot: 1 Yes, limited a little: 2 No, not limited at all: 3
3d. Climbing several flight of stairs	Physical Functioning (PF)	Yes, limited a lot: 1 Yes, limited a little: 2 No, not limited at all: 3
3e. Climbing one flight of stairs	Physical Functioning (PF)	Yes, limited a lot: 1 Yes, limited a little: 2 No, not limited at all: 3
3f. Bending, kneeling or stooping	Physical Functioning (PF)	Yes, limited a lot: 1 Yes, limited a little: 2 No, not limited at all: 3
3g. Walking more than a mile	Physical Functioning (PF)	Yes, limited a lot: 1 Yes, limited a little: 2 No, not limited at all: 3
3h. Walking several hundred yards	Physical Functioning (PF)	Yes, limited a lot: 1 Yes, limited a little: 2 No, not limited at all: 3
3i. Walking one hundred yards	Physical Functioning (PF)	Yes, limited a lot: 1 Yes, limited a little: 2 No, not limited at all: 3
3j. Bathing or dressing yourself	Physical Functioning (PF)	Yes, limited a lot: 1 Yes, limited a little: 2 No, not limited at all: 3
4. During the past 4 weeks, how much of the time have you had any of the following problems with your work or other regular daily activities as a result of your physical health?		
4a. Cut down on the amount of time you spent on work or other activities	Role-Physical (RP)	All of the time: 1 Most of the time: 2 Some of the time: 3 A little of the time: 4 None of the time: 5
4b. Accomplished less than you would like	Role-Physical (RP)	All of the time: 1 Most of the time: 2 Some of the time: 3 A little of the time: 4 None of the time: 5
4c. Were limited in the kind of work or other activities	Role-Physical (RP)	All of the time: 1 Most of the time: 2 Some of the time: 3 A little of the time: 4 None of the time: 5
4d. Had difficulty performing the work or other activities (for example, it took extra effort)	Role-Physical (RP)	All of the time: 1 Most of the time: 2 Some of the time: 3 A little of the time: 4 None of the time: 5
5. During the past 4 weeks, how much of the time have you had any of the following problems with your work or other regular daily activities as a result of any emotional problems (such as feeling depressed or anxious)?		

Question	Domain	Score
5a. Cut down on the amount of time you spent on work or other activities.	Role-Emotional (RE)	All of the time: 1 Most of the time: 2 Some of the time: 3 A little of the time: 4 None of the time: 5
5b. Accomplished less than you would like	Role-Emotional (RE)	All of the time: 1 Most of the time: 2 Some of the time: 3 A little of the time: 4 None of the time: 5
5c. Did work or other activities less carefully than usual	Role-Emotional (RE)	All of the time: 1 Most of the time: 2 Some of the time: 3 A little of the time: 4 None of the time: 5
6. During the past 4 weeks, to what extent has your physical health or emotional problems interfered with your normal social activities with family, friends, neighbours or groups?	Social Functioning (SF)	Not at all: 5 Slightly: 4 Moderately: 3 Quite a bit: 2 Extremely: 1
7. How much bodily pain have you had during the past 4 weeks?	Bodily Pain (BP)	None: 6 Very mild: 5.4 Mild: 4.2 Moderate: 3.1 Severe: 2.2 Very severe: 1
8. During the past 4 weeks, how much did pain interfere with your normal work (including both work outside the home and housework)?	Bodily Pain (BP)	If Question 7 Answered: Not at all (and Question 7 = None): 6 Not at all (and Question 7 not None): 5 A little bit: 4 Moderately: 3 Quite a bit: 2 Extremely: 1 If Question 7 Not Answered: Not at all: 6 A little bit: 4.75 Moderately: 3.5 Quite a bit: 2.25 Extremely: 1
9. These questions are about how you feel and how things have been with you during the past 4 weeks. For each question, please give the one answer that comes closest to the way you have been feeling. How much of the time during the past 4 weeks...		
9a. Did you feel full of life?	Vitality (VT)	All of the time: 5 Most of the time: 4 Some of the time: 3 A little of the time: 2 None of the time: 1
9b. Have you been very nervous?	Mental Health (MH)	All of the time: 1 Most of the time: 2 Some of the time: 3 A little of the time: 4 None of the time: 5

Question	Domain	Score
9c. Have you felt so down in the dumps that nothing could cheer you up?	Mental Health (MH)	All of the time: 1 Most of the time: 2 Some of the time: 3 A little of the time: 4 None of the time: 5
9d. Have you felt calm and peaceful?	Mental Health (MH)	All of the time: 5 Most of the time: 4 Some of the time: 3 A little of the time: 2 None of the time: 1
9e. Did you have a lot of energy?	Vitality (VT)	All of the time: 5 Most of the time: 4 Some of the time: 3 A little of the time: 2 None of the time: 1
9f. Have you felt downhearted and depressed?	Mental Health (MH)	All of the time: 1 Most of the time: 2 Some of the time: 3 A little of the time: 4 None of the time: 5
9g. Did you feel worn out?	Vitality (VT)	All of the time: 1 Most of the time: 2 Some of the time: 3 A little of the time: 4 None of the time: 5
9h. Have you been happy?	Mental Health (MH)	All of the time: 5 Most of the time: 4 Some of the time: 3 A little of the time: 2 None of the time: 1
9i. Did you feel tired?	Vitality (VT)	All of the time: 1 Most of the time: 2 Some of the time: 3 A little of the time: 4 None of the time: 5
10. During the past 4 weeks how much of the time has your physical health or emotional problems interfered with your social activities (like visiting friends, relatives etc.)?	Social Functioning (SF)	All of the time: 1 Most of the time: 2 Some of the time: 3 A little of the time: 4 None of the time: 5
11. How true or false is each of the following statements for you?		
11a. I seem to get sick a little easier than other people	General Health (GH)	Definitely true: 1 Mostly true: 2 Don't know: 3 Mostly false: 4 Definitely false: 5
11b. I am as healthy as anybody I know	General Health (GH)	Definitely true: 5 Mostly true: 4 Don't know: 3 Mostly false: 2 Definitely false: 1
11c. I expect my health to get worse	General Health (GH)	Definitely true: 1 Mostly true: 2 Don't know: 3 Mostly false: 4 Definitely false: 5

Question	Domain	Score
11d. My health is excellent	General Health (GH)	Definitely true: 5 Mostly true: 4 Don't know: 3 Mostly false: 2 Definitely false: 1

After scores have been assigned as in Table 3, raw scores for each domain should be calculated as set out in Table 4.

Table 4 SF-36 Scoring for Domains

Domain	Items to Sum	Lowest and Highest Possible Score	Possible Raw Score Range
Physical Functioning (PF)	3a + 3b + 3c + 3d + 3e + 3f + 3g + 3h + 3i + 3j	10, 30	20
Role-Physical (RP)	4a + 4b + 4c + 4d	4, 20	16
Bodily Pain (BP)	7 + 8	2, 12	10
General Health (GH)	1 + 11a + 11b + 11c + 11d	5, 25	20
Vitality (VT)	9a + 9e + 9g + 9i	4, 20	16
Social Functioning (SF)	6 + 10	2, 10	8
Role-Emotional (RE)	5a + 5b + 5c	3, 15	12
Mental Health (MH)	9b + 9c + 9d + 9f + 9h	5, 25	20

The following derivations will be made based of the subject diary reported results:

- The score for each domain should be transformed to a 0 – 100 range using the following formula:

$$Transf. Domain = \frac{[(Actual Raw Score - Lowest Possible Raw Score)]}{Possible Raw Score Range} \times 100$$

- A z-score standardization of the SF-36 transformed domain scores should be determined as follows:

$$PF_z = \frac{PF - 83.29094}{23.75883}$$

$$RP_z = \frac{RP - 82.50964}{25.52028}$$

$$BP_z = \frac{BP - 71.32527}{23.66224}$$

$$GH_z = \frac{GH - 70.84570}{20.97821}$$

$$\circ VT_z = \frac{VT-58.31411}{20.01923}$$

$$\circ SF_z = \frac{SF-84.30250}{22.91921}$$

$$\circ RE_z = \frac{RE-87.39733}{21.43778}$$

$$\circ MH_z = \frac{MH-74.98685}{17.75604}$$

- After the z-scores have been determined, the z-scores will be used to determine norm-based scores that will be presented in listings and summaries. The norm based scores should be determined as:

$$XX_N = 50 + (XX_z \times 10)$$

where XX represents the difference domains (PF, RP, BP, GH, VT, SF, RE and MH).

- The raw aggregate summary scores for the physical and mental components are determined as follows:
 - $AGG_{phys} = (PF_z \times 0.42402) + (RP_z \times 0.35119) + (BP_z \times 0.31754) + (GH_z \times 0.24954) + (VT_z \times 0.02877) + (SF_z \times (-0.00753)) + (RE_z \times (-0.19206)) + (MH_z \times (-0.22069))$
 - $AGG_{ment} = (PF_z \times (-0.22999)) + (RP_z \times (-0.12329)) + (BP_z \times (-0.09731)) + (GH_z \times (-0.01571)) + (VT_z \times 0.23534) + (SF_z \times 0.26876) + (RE_z \times 0.43407) + (MH_z \times 0.48581)$
- The normalized aggregate scores that will be presented in listings and summaries are determined as:

$$YY_N = 50 + (AGG_{YY} \times 10)$$

where YY is either the physical component score or mental component score.

- Any domain with less than half of the questions answered will have no score calculated. For scales with any questions not answered, but with more than half of

the questions answered, the raw scale should be adjusted in terms of the lowest and highest possible score, including the possible raw range. All other scores will be affected by this change in transformed score. As an example, if question 3a is not answered, then the lowest score for physical functioning is to change from 10 to 9, the highest score is to change from 30 to 27 and the possible raw range from 20 to 18. The new values will be used in determining the transformed score for physical functioning.

Within treatment arm change and between treatment arm change in SF-36 total score as well as the physical and mental component scores between baseline and completion will be tested for any statistical significant differences in a similar manner as described in Section 7.2.1: Haemophilia Joint Health Score (HJHS) Questionnaire.

Items to be included in these tests as part of the secondary efficacy outcomes are:

- Change in physical domain component scores.

Items to be included in these tests as part of the exploratory efficacy outcomes are:

- Change in mental domain component scores.

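### The SF-36 missing-item rule does not cover a domain with exactly half its items answered; read literally, one-item Bodily Pain runs from 40 to -10 instead of 100 to 0

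*SAP*

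**What the plan says.** SAP 7.2.3 scores the SF-36 in steps. Table 3 gives item scores. Table 4 sums them by domain and lists the lowest and highest possible sums and the range; the Bodily Pain row reads "Bodily Pain (BP) 7 + 8 2, 12 10". The raw sum is then rescaled: "The score for each domain should be transformed to a 0 – 100 range using the following formula". The formula is (raw - lowest) / range x 100. The result is standardised, put on a 50 + 10z scale, and weighted into the physical and mental component scores.

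The missing-item rule has two parts:

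- No score: "Any domain with less than half of the questions answered will have no score calculated".
- Adjustment: the condition begins "For scales with any questions not answered, but with more than half of" and refers to the items present; only then are the bounds of the raw sum shortened, and the range with them. The example is Question 3a unanswered, where Physical Functioning changes from 10, 30 and 20 to 9, 27 and 18.

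Table 3 also has a separate set of Question 8 values headed "If Question 7 Not Answered", so the SAP expects Bodily Pain to be scored from one item.

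**The concern.** One limit is set below half and the other above half, so exactly half falls between them. The domain is not excluded, and the only sentence that shortens the range does not reach it.

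This is not a remote case. Bodily Pain and Social Functioning have two items each, so one skipped item is always exactly half, and the adjustment as worded can never operate for them. Physical Functioning (5 of 10), Role-Physical (2 of 4) and Vitality (2 of 4) can also reach it. General Health, Role-Emotional and Mental Health have odd item counts and cannot.

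The SF-36 physical domain and component scores are the listed secondary patient-reported outcome (Protocol 8.4.2.3, SAP 3.1.2.3), and SAP 7.2.3 tests their change within and between arms. A score that is too low at one visit distorts that subject's change. Two programmers could also follow the same text to different values.

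**Working it through.** **Inputs (all SAP 7.2.3).** Item minima and maxima from Table 3; item counts, lowest scores and ranges from Table 4; the domain means and SDs used for the z-scores; the weights for the physical component.

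**Reproducing the plan's figures.** Take lowest = items answered x item minimum, highest = items answered x item maximum, range = highest - lowest. This returns every Table 4 row. For Physical Functioning with 3a missing it gives 9 x 1 = 9, 9 x 3 = 27 and 27 - 9 = 18, as the SAP states.

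**Bodily Pain, one of two items answered.** Each item runs from 1 to 6.

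- Unadjusted (lowest 2, range 10): best (6 - 2)/10 x 100 = 40; worst (1 - 2)/10 x 100 = -10.
- Adjusted (lowest 1, range 5): best (6 - 1)/5 x 100 = 100; worst (1 - 1)/5 x 100 = 0.

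These end points are the same whether the answered item is Question 7 or Question 8. The effect on the physical component is 10 x 0.31754 / 23.66224 = 0.1342 points per domain point. With Question 8 alone:

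| Question 8 value | Unadjusted | Adjusted | Physical component too low by |
|---|---|---|---|
| 6 | 40 | 100 | 60 x 0.1342 = 8.05 |
| 4.75 | 27.5 | 75 | 47.5 x 0.1342 = 6.37 |
| 3.5 | 15 | 50 | 35 x 0.1342 = 4.70 |
| 2.25 | 2.5 | 25 | 22.5 x 0.1342 = 3.02 |
| 1 | -10 | 0 | 10 x 0.1342 = 1.34 |

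At the best answer the norm-based Bodily Pain score is 50 + 10 x (40 - 71.32527)/23.66224 = 36.8. Adjusted, it is 50 + 10 x (100 - 71.32527)/23.66224 = 62.1.

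**All domains that can be exactly half answered.** Adjusted scores are 100 (best) and 0 (worst) in every row. The component shift is 10 x weight x (unadjusted - adjusted) / SD.

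| Domain | Items skipped | Unadjusted best / worst | Weight, SD | Physical component shift, best / worst |
|---|---|---|---|---|
| Bodily Pain | 1 of 2 | 40 / -10 | 0.31754, 23.66224 | -8.05 / -1.34 |
| Social Functioning | 1 of 2 | 37.5 / -12.5 | -0.00753, 22.91921 | +0.21 / +0.04 |
| Role-Physical | 2 of 4 | 37.5 / -12.5 | 0.35119, 25.52028 | -8.60 / -1.72 |
| Vitality | 2 of 4 | 37.5 / -12.5 | 0.02877, 20.01923 | -0.90 / -0.18 |
| Physical Functioning | 5 of 10 | 25 / -25 | 0.42402, 23.75883 | -13.39 / -4.46 |

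Social Functioning matters more for the exploratory mental component, where its weight is 0.26876. At the best answer that component is too low by 10 x 0.26876 x 62.5 / 22.91921 = 7.3 points.

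**Evidence of intent.** The Question 8 values for a missing Question 7 are equally spaced from 1 to 6. They map to 100, 75, 50, 25 and 0 only with the one-item range of 5.

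**The case against.** The strongest reply is that the SAP never instructs anyone to keep the full range. It is silent at exactly half, and three readings are open: no score, adjust, or leave unadjusted. The unadjusted reading fits the rest of the section worst, because it gives negative values on a 0-100 scale and defeats the purpose of the special Question 8 values. A careful programmer might adjust anyway. This stands: the full range follows from silence, not from an order. It does not remove the defect, since no other text closes the gap.

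A reader might also infer that any skipped item pulls the Physical Component Score down by many points. The documents do not support that. One skipped item has a material effect on that score only through Bodily Pain. The Role-Physical and Physical Functioning figures need two and five skipped items, and their largest values assume best answers throughout.

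Nor does the error always appear as a fall. An item skipped at completion gives a spurious fall in change; one skipped at baseline gives a spurious rise. Entry into the tests is not automatic either, because SAP 7.2.1 admits only changes above half the baseline SD. The largest Bodily Pain error clears that limit unaided only if the baseline SD of the physical component is below 2 x 8.05 = 16.1. The smallest does so only if the SD is below 2 x 1.34 = 2.7. The documents give no baseline SD. If the filter is read as signed, a spurious fall would not enter at all.

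Finally, there are safeguards. The investigator reviews the diary for completeness and asks for missing information (Protocol 10.5), and SAP 7.2 lists SF-36 scores as well as item responses among the vendor's data. Both may reduce how often the gap bites. Neither settles it, because SAP 7.2.3 still specifies its own derivation.

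**Conclusion.** Wrong as written, and minor. A half-answered domain is neither dropped nor adjusted. Read literally, one-item Bodily Pain scores 40 to -10 instead of 100 to 0, and the Physical Component Score at that visit is about 8.1 to 1.3 points too low. For the two-item domains the adjustment can never apply, although Table 3 shows that Bodily Pain is meant to be scored in this case.

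The size rests on the literal reading and on the other domains being complete. It is an error per affected subject and visit; the effect on the arm comparison cannot be estimated, because the documents do not give the frequency of skipped items. The primary endpoint is unaffected.

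**What to change.** In the missing-item rule of SAP 7.2.3, make the adjustment apply when at least half of a domain's questions are answered, in place of more than half. The method of the Question 3a example then covers every case that receives a score. One-item Bodily Pain takes lowest 1, highest 6 and range 5, and stays within 0-100. The wording would agree with the Haemo-SYM rule in SAP 7.2.2, which scores a subscale when at least 50% of its results are available.

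The cost is two words in the SAP and a check that the scoring program follows them. No new data are needed.

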7.2.4 Euro Quality of Life-5 Dimension (EQ-5D) Questionnaire

The EQ-5D questionnaire is a self-administered, standardized instrument for the measurement of health status regards quality of life.

The EQ-5D comprises 5 dimensions of health (mobility, self-care, usual activities, pain/discomfort, and anxiety/depression). For each dimension, respondents select which statement best describes their health on that day from a possible 5 options of increasing levels of severity with a score from 1 to 5 (no problems, slight problems, moderate problems, severe problems, and extreme problems). The severity score on each individual dimension is combined to form a unique EQ-5D health state as a 5-digit code allowing for a total of 3125 health states.

For example, state 11111 indicates no problems on any of the 5 dimensions. These data will be converted into a weighted health state index by applying scores from EQ-5D value sets elicited from general population samples (the base case will be the United Kingdom valuation set, with other country value sets applied as available).

In addition to the descriptive system, subjects also assess their health on the day of assessment on a visual analogue scale (VAS), ranging from 0 (worst imaginable health) to 100 (best imaginable health). This score is reported separately.

Information on the EQ-5D is obtained from electronic subject diaries as supplied by the third party vendor eRT.

The following derivations will be made based of the subject diary reported results:

- The unique 5-digit health code per subject per assessment which is obtained by concatenating the individual scores of the five domains in their order as presented on the questionnaire itself.
- The utility total score should only be derived and calculated as follows if none of the 5 component scores are missing (depending on the country/region applicable) using both “VAS” value sets and the TTO value sets:
 - For all countries excluding Germany, the utility total score using “VAS” value sets can be derived as:

Utility Total Score

$$\begin{aligned}
 &= W_{FH} + W_{N2} \times N2 + W_{N3} \times N3 + W_{MO2} \times MO2 \\
 &+ W_{MO3} \times MO3 + W_{SC2} \times SC2 + W_{SC3} \times SC3 \\
 &+ W_{UA2} \times UA2 + W_{UA3} \times UA3 + W_{PD2} \times PD2 \\
 &+ W_{PD3} \times PD3 + W_{AD2} \times AD2 + W_{AD3} \times AD3
 \end{aligned}$$

where the variables above are defined below in Table 5 and Table 6:

Table 5 EQ-5D Variable Definitions

Condition	Condition Code (Possible Values: 0 and 1)	Weight Name
Full health (11111)		W_FH
At least one 2 or 3 (N2)	N2	W_N2
At least one 3 (N3)	N3	W_N3
Mobility = 2	MO2	W_MO2
Mobility = 3	MO3	W_MO3
Self Care = 2	SC2	W_SC2
Self Care = 3	SC3	W_SC3
Usual Activities = 2	UA2	W_UA2

Condition	Condition Code (Possible Values: 0 and 1)	Weight Name
Usual Activities = 3	UA3	W_UA3
Pain/Discomfort = 2	PD2	W_PD2
Pain/Discomfort = 3	PD3	W_PD3
Anxiety/Depression = 2	AD2	W_AD2
Anxiety/Depression = 3	AD3	W_AD3

Table 6 EQ-5D VAS Value Sets (Excluding Germany)

Weight Name	Belgium	Denmark	Europe	Finland	New Zealand	Slovenia	Spain	UK
W_FH	1	1	1	1	1	1	1	1
W_N2	-0.152	-0.225	-0.1279	-0.158	-0.2041	-0.128	-0.1502	-0.155
W_N3	-0.256	0	-0.2288	0	-0.2165	0	-0.2119	-0.215
W_MO2	-0.074	-0.126	-0.0659	-0.058	-0.0753	-0.206	-0.0897	-0.071
W_MO3	-0.148	-0.252	-0.1829	-0.230	-0.1506	-0.412	-0.1794	-0.182
W_SC2	-0.083	-0.112	-0.1173	-0.098	-0.0714	-0.093	-0.1012	-0.093
W_SC3	-0.166	-0.224	-0.1559	-0.143	-0.1428	-0.186	-0.2024	-0.145
W_UA2	-0.031	-0.064	-0.0264	-0.047	-0.0136	-0.054	-0.0551	-0.031
W_UA3	-0.062	-0.128	-0.0860	-0.131	-0.0272	-0.108	-0.1102	-0.081
W_PD2	-0.084	-0.078	-0.0930	-0.111	-0.0798	-0.111	-0.0596	-0.084
W_PD3	-0.168	-0.156	-0.1637	-0.153	-0.1596	-0.222	-0.1192	-0.171
W_AD2	-0.103	-0.091	-0.0891	-0.160	-0.0920	-0.093	-0.0512	-0.063
W_AD3	-0.206	-0.182	-0.1290	-0.196	-0.1840	-0.186	-0.1024	-0.124

- For Germany, the utility total score using the “VAS” value set can be derived as:

Utility Total Score

$$\begin{aligned}
 &= W_{FH} \times W_{N2}^{N2} \times W_{MO2}^{MO2} \\
 &\quad \times W_{MO3}^{MO3} \times W_{SC2}^{SC2} \times W_{SC3}^{SC3} \\
 &\quad \times W_{UA2}^{UA2} \times W_{UA3}^{UA3} \\
 &\quad \times W_{PD2}^{PD2} \times W_{PD3}^{PD3} \times W_{AD2}^{AD2} \\
 &\quad \times W_{AD3}^{AD3}
 \end{aligned}$$

where the variables above are defined in Table 5 and Table 7:

Table 7 EQ-5D Vas Values for Germany

Weight Name	Germany
W_FH	1
W_N2	0.9256
W_MO2	0.9447
W_MO3	0.3927
W_SC2	0.808
W_SC3	0.4702
W_UA2	0.8803
W_UA3	0.5538
W_PD2	0.9745
W_PD3	0.4671
W_AD2	0.8174
W_AD3	0.4682

- For all countries excluding the US, the utility total score using “TTO” value sets can be derived as:

Utility Total Score

$$\begin{aligned}
 &= W_{FH} + W_{N2} \times N2 + W_{N3} \times N3 + W_{MO2} \times MO2 \\
 &+ W_{MO3} \times MO3 + W_{SC2} \times SC2 + W_{SC3} \times SC3 \\
 &+ W_{UA2} \times UA2 + W_{UA3} \times UA3 + W_{PD2} \times PD2 \\
 &+ W_{PD3} \times PD3 + W_{AD2} \times AD2 + W_{AD3} \times AD3
 \end{aligned}$$

where the variables above are defined in Table 5 and Table 8 .

Table 8 EQ-5D TTO Value Sets (Excluding USA)

Weight Name	Denmark	Germany	Japan	Netherlands	Spain	UK	Zimbabwe
W_FH	1	1	1	1	1	1	1
W_N2	-0.114	-0.001	-0.152	-0.071	-0.024	-0.081	-0.100
W_N3	0	-0.323	0	-0.234	-0.291	-0.269	0
W_MO2	-0.053	-0.099	-0.075	-0.036	-0.106	-0.069	-0.056
W_MO3	-0.411	-0.327	-0.418	-0.161	-0.43	-0.314	-0.204
W_SC2	-0.063	-0.087	-0.054	-0.082	-0.134	-0.104	-0.092
W_SC3	-0.192	-0.174	-0.102	-0.152	-0.309	-0.214	-0.231
W_UA2	-0.048	0	-0.044	-0.032	-0.071	-0.036	-0.043
W_UA3	-0.144	0	-0.133	-0.057	-0.195	-0.094	-0.135
W_PD2	-0.062	-0.112	-0.08	-0.086	-0.089	-0.123	-0.067
W_PD3	-0.396	-0.315	-0.194	-0.329	-0.261	-0.386	-0.302
W_AD2	-0.068	0	-0.063	-0.124	-0.062	-0.071	-0.046
W_AD3	-0.367	-0.065	-0.112	-0.325	-0.144	-0.236	-0.173

- For USA, the utility total score using the “TTO” value set can be derived as:

$$Utility\ Total\ Score = W_{FH} + W_{MO2} \times MO2 + W_{MO3} \times MO3 + W_{SC2} \times SC2 + W_{SC3} \times SC3 + W_{UA2} \times UA2 + W_{UA3} \times UA3 + W_{PD2} \times PD2 + W_{PD3} \times PD3 + W_{AD2} \times AD2 + W_{AD3} \times AD3 + W_{D1} \times D1 + W_{I2_SQ} \times I2_SQ + W_{I3} \times I3 + W_{I3_SQ} \times I3_SQ$$

where the variables above are defined in Table 5, Table 9 and Table 10:

Table 9 EQ-5D USA Additional Variable Definitions

Variable Description	Variable	Possible Values	Weight
Number of movements away from full health beyond the first	D1	0, 1, 2, 3, 4	$W_{D1} = 0.140$
Square if I2 (I2 = Number of dimensions at level 2 beyond the first)	I2_SQ	0, 1, 4, 9, 16	$W_{I2_SQ} = -0.011$
Number of dimensions at level 3 beyond the first	I3	0, 1, 2, 3, 4	$W_{I3} = 0.122$
Square if I3	I3_SQ	0, 1, 4, 9, 16	$W_{I3_SQ} = 0.015$

Table 10 EQ-5D VAS Values for USA

Weight Name	USA
W_FH	1
W_MO2	-0.146
W_MO3	-0.558
W_SC2	-0.175
W_SC3	-0.471
W_UA2	-0.14
W_UA3	-0.374
W_PD2	-0.173
W_PD3	-0.537
W_AD2	-0.156
W_AD3	-0.45

Within treatment arm change and between treatment arm change in EQ-5D utility total score as well as the VAS score between baseline and completion will be tested for any statistical significant differences in a similar manner as described in Section 7.2.1: Haemophilia Joint Health Score (HJHS) Questionnaire.

The following EQ-5D total scores form part of both the secondary and exploratory efficacy outcomes:

- Utility total score.
- VAS score.

